#### 4.3.1 Cohort recruitment and follow-up

Prior to the Y-Check visit, programme participants will be invited to join the research cohort and agree to the following additional activities:

- Self-completion of an additional module of the pre-consultation questionnaire (to measure baseline outcomes not captured for programme participants e.g. knowledge, intention, agency, educational outcomes)
- Observation of check-up visit and referral visit procedures by a Y-Check team member.
- Exit interviews
- Follow up visits at 4-months and 12-months (questionnaire and screening tests)
- Potential participation in qualitative interviews or group activities

Y-Check 1: The information sheet distributed by the school about the check-up visits (section 3.7) will include information about the Y-Check research cohort and the need for separate consent to participate in the research study. Eligible students will be asked to return completed informed parental consent and individual assent forms either before or on the day of the check-up visit.

Eligibility criteria will be:

- Currently enrolled in Grade 5, 6 or 7 in one of the study primary schools
- Adolescent and their parent/guardian have consented/assented to participate in the check-up visit
- Written informed parental/guardian consent and client assent to participate in the research study

Y-Check 2: The information sheet distributed by the school about the check-up visits (section 3.7) will include information about the Y-Check research cohort and the need for separate consent to participate in the research study. Eligible students will be asked to return their completed informed consent form either before or on the day of the check-up visit.

In the community, mobilisation and advertisement will encourage adolescents to attend the community hubs for check-up visits and will describe the accompanying research study. At the community hubs,

following confirmation of eligibility, clients will be asked to provide written informed consent to participate in the research study.

Eligibility criteria will be:

#### Schools:

- Currently enrolled in Form 3, 4 or 5 in one of the study secondary schools
- Adolescent and their parent/guardian have consented/assented to participate in the check-up visit
- Written informed parental/guardian consent and client assent to participate in the research study Community hub:
- Currently aged 16 to 19 years & resident in the study community
- Adolescent has consented to participate in some or all components of the check-up visit
- Written informed consent from client to participate in the research study

Cohort follow-up visits will be at schools for Y-Check 1 participants, and at the school and/or community hubs for Y-Check 2 participants, using SMS reminders and active follow-up. Follow-up of Y-Check 1 clients may also be done using the contact details provided by parents/carers. Y-Check 2 clients will be asked to provide mobile phone numbers so that they can receive reminders about referrals and a monthly health message during the 12-month follow-up period. USD5 will be given to each participant to cover any transport costs that they might have incurred to attend follow-up visits.

#### 4.3.2 Outcome evaluation

Adolescent outcomes (see **Figure 1, section 6.1**) will be ascertained during the check-up screening visit, through 4-month and 12-month follow-up visits and through review of school and health service registers and/or collection of referral vouchers. The primary outcome will be measured at the initial check-up visit and through recovery of referral vouchers within the 4-month follow-up period. The 12-month follow-up will provide preliminary data on longer-term health, well-being and education outcomes, and will inform the feasibility of longer-term follow-up in future planned phases of the research.

The primary outcome will be the proportion of those screening positive for at least one condition who receive appropriate on-the-spot care or complete appropriate referral for all identified conditions within 4 months. Completed referral is defined as attending at least the first referral appointment. We expect referral/treatment to have occurred within 4 months (**Figure 1**). Monitoring of completed referral will be facilitated by recovering vouchers given to participants to allow them to access referral services for free and through a review of health records and registers. At follow-up visits, clients will also be asked to report on their attendance at health services in the previous 4 or 12 months.

Secondary implementation outcomes will be yield of previously undiagnosed and un-referred conditions clinical outcomes among those who screen positive, and intervention acceptability, adoption, appropriateness, feasibility, fidelity and cost (**Figure 1**, section 4.3.3 **Process evaluation**).

Secondary client outcomes will be knowledge about health services and health behaviours, agency to make decisions about health, reported health-related risk and protective behaviours, reported engagement with health services, well-being, self-esteem and quality of life, clinical outcomes,

educational outcomes, client-centered outcomes (see section 2.3) and cost-effectiveness of the intervention (**Figure 1**).

Following the initial check-up screening visit, and during 4-month and 12-month follow-up visits, clients will be asked to self-complete a tablet questionnaire, and undergo clinical screening tests. The content of the follow-up visits will be decided on during Phase 1 following piloting and costing of the screening and referral protocols for each condition. The follow-up visits may offer a reduced number of clinical screening tests.

#### 4.3.3 Process Evaluation

We will conduct a mixed-methods process evaluation based on the MRC Process Evaluation framework. Several research questions and key areas of investigation will be addressed related to each of the 3 core process evaluation functions: implementation, mechanisms of impact and context. We will draw on implementation and evaluation frameworks (RE-AIM, CFIR^49, PRISM) to guide the selection of implementation outcomes and contextual factors, develop interview guides, and guide the coding and analysis of barriers and facilitators to programme implementation. Implementation outcomes of interest are acceptability, adoption, appropriateness, feasibility, and fidelity (**Figure 1**).

Across the pilot and intervention studies, data collection will include observations and real-time feedback, quantitative process data, focus group discussions and in-depth interviews with adolescents, those involved in intervention delivery, and other stakeholders. Data will be collected at multiple time points, using multiple methods and sources and triangulated with outcome data. To help interpret the results of the study, existing adolescent services will be mapped in the study communities. The process evaluation findings will provide guidance for the next stage of the programme and potential future sustainable and scalable implementation by local health authorities should it prove successful.

The research questions and key areas of investigation, along with the related data collection methods and sources are outlined in detail in **Table 2**.

#### Quantitative data

There will be several sources of quantitative process data. Routine Y-Check programme data will be collected from all intervention sites. To the degree possible, the study team will obtain data from routine records in health facilities and other community based organisations (CBOs). This will take the form of de-identified, aggregate routinely-reported health facility data on the uptake of health services by adolescents before, during and after the Y-Check implementation period. The data will be requested from the specific clinics who are providing the referral services for Y-Check participants. As mentioned, it will be aggregate, routinely-reported data and as such it will be number of adolescents seen. It will allow us to to estimate how much the Y-Check referrals increase the number of adolescents attending these clinics, to better understand service use, the number of Y-Check service attendances and uptake of specific service components will be recorded. Outputs of interest include the proportion attending, yield of new cases, diagnostic accuracy of screening tests, screening uptake, and prevalence of conditions. Data on reported uptake of and acceptability of services will be obtained after the initial check-up visit and during the 4- and 12- month client follow-up visits.

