#### Finalisation of screening and referral protocols

We will liaise with MoHCC and other service providers to establish referral pathways for the conditions listed in Table 1. Potential referral institutions will be visited by the study team to understand the services that they offer, the services that they could potentially offer with additional resources, and to assess the quality of the services provided by comparing against national guidelines and standards. Referral pathways will be pre-tested to assess their local acceptability. Referred clients will be given a voucher to allow them to access referral services for free. Redeemed vouchers will be retrieved by the study team and used to measure referral uptake and organise payment to the providers. Additional support for the completion of referrals and access to care will be developed in collaboration with the YAG and CSC. One potential mechanism of providing advice and support to adolescents and their parents/guardians is through a free hotline number, similar to the one currently used in the CHIEDZA trial.

The output will be finalised screening and referral protocols to be used in the pilot study.

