Self-completed questionnaire and provider recorded treatment/counselling services	Age, sex, school/hub, screening test data, screening results, treatments received, and referrals provided for a range of conditions and behaviours.  HIV oral mucosal transudate and STI test results from a maximum of 1100 adolescents aged 16.10 years.	Client verbal consent for use of de- identified data for programme monitoring and improvement purposes. (Y-Check 2 at community hubs)
	adolescents aged 16-19 years.	Parent/guardian written consent and participant written assent for Y-

	Backend digital platform data: information	Check 1 and Y-Check 2 (school-	
	viewed, games played, data from screening apps, rewards provided/used etc.	recruitment).	
Y-CHECK referral &	Referral voucher with ID number, sex, age	Client verbal consent for	
referral service	and reason for referral	information to be shared with	
attendance	Timing of uptake of service within 0-4 months post check-up visit linked to ID	service providers (Y-Check 2 at community hubs)	
		Parent/guardian written consent and participant written assent for Y-	
		Check 1 and Y-Check 2 (school-	
		recruitment).	
Additional	Cost data	None	
programme			
monitoring data			
	Outcomes and evaluation		
Pilot study &	Self-reported questionnaire data	Client written informed consent.	
Cohort study	(demographics, location data, contact	(Y-Check 2 at community hubs)	
	details, study outcomes not captured in		
	programme data including knowledge,	Parent/guardian written consent	
	reported behaviour, well-being and self-	and participant written assent for Y-	
	esteem, acceptability and reported uptake	Check 1 and Y-Check 2 (school-	
	of services)	recruitment).	
Adolescents and	Sociodemographic data, audio-taped	Participant written informed	
stakeholders	interviews, transcripts of IDIs, paired/group	consent.	
(adolescents	interviews and / or FGDs		
providers, family	Process evaluation data on the	Parent/guardian written consent	
members of	implementation, mechanisms of impact and	and participant written assent for Y-	
adolescents,	context of the intervention	Check 1 and Y-Check 2 (school-	
community	Notes from structured / unstructured	recruitment) only.	
members)	observations		
	Annonymised meeting/workshop		
	attendance registers (affiliation, sex, age)		

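### Before/during/after counts from the referral clinics alone cannot show how much Y-Check referrals raise attendance; vouchers and register matches can show the gross load

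*Protocol*

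**What the plan says.** Section 4.3.3 (Quantitative data) describes the source as "aggregate routinely-reported health facility data on the uptake of health services by adolescents before, during and after the Y-Check implementation period". On where it comes from: "The data will be requested from the specific clinics who are providing the referral services for Y-Check participants". On its content: "it will be aggregate, routinely-reported data and as such it will be number of adolescents seen". The stated use is to "estimate how much the Y-Check referrals increase the number of adolescents attending these clinics". The same run-on sentence adds that Y-Check service attendances and uptake of service components will be recorded, without saying how these enter the estimate.

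A second source is set up elsewhere in the protocol. Section 4.2 (Finalisation of screening and referral protocols) says: "Redeemed vouchers will be retrieved by the study team and used to measure referral uptake and organise payment to the providers". Table 3 in section 5.3 lists a "Referral voucher with ID number, sex, age" and the reason for referral, together with "Timing of uptake of service within 0-4" months after the check-up, linked to the ID. Section 4.3.2 supplements the vouchers with a review of health records and registers and with self-report at follow-up. It counts a referral as complete once the first appointment has been attended. Nothing ties the estimate in section 4.3.3 to these records.

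**The concern.** The target is causal: the increase due to referrals. The data are one uncontrolled series of totals per clinic. No comparison clinics are named, no adjustment for trend is mentioned, and Y-Check clients cannot be picked out of the totals.

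The protocol also describes other programme activity that could move the same counts. Section 3.5 gives referral services training and support in youth-friendly care. Section 3.7 adds mobile outreach, section 3.7.1 materials on navigating the health system, and section 4.3.1 a monthly health message to Y-Check 2 clients. A real rise in attendance might therefore come from the programme without coming from its referrals, or from neither. A general fall could hide a real referral effect.

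Section 4.3.3 says the process evaluation will guide possible sustainable and scalable implementation by local health authorities. A clinic-load figure wrongly assigned to referrals would mislead those users.

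**Working it through.** The protocol states no figure for this effect, its baseline or its precision, so there is nothing to reproduce.

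**Step 1: what each source measures.** Write the change in a clinic's total as

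D = (V − A) + S + T

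where V is referral visits by Y-Check clients, A is those among them that would have happened anyway, S is other visits raised or lowered by the programme (training, outreach, messages, spill-over), and T is change unrelated to the programme. The aggregate series gives D only. Section 4.3.3 asks for V − A. Without comparison clinics T is not separable, and even with them S would remain mixed in. Vouchers and register matches approximate V, but not A.

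**Step 2: the likely size of V.** Inputs from the protocol: four age-by-gender groups, 150 of 500 screening positive in each, 75% managed (section 6.2); four public primary facilities (section 3.2); four quarters of implementation, i.e. 12 months (Figure 2).

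- Screening positive: 4 × 150 = 600.
- Managed: 0.75 × 600 = 450.
- If all were managed by one clinic visit: 450 / (12 × 4) = 9.4 per clinic-month. Over 16 months, which adds the 4-month referral window: 450 / (16 × 4) = 7.0.
- If half were managed by referral: 225 / 48 = 4.7. If a quarter: 112.5 / 48 = 2.3.

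**Step 3: when ordinary change equals V.** Break-even yearly baseline = V / proportional change. Dividing by 48 gives visits per clinic-month. The sizes of change are assumptions.

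| V | 5% change | 10% change | 20% change |
|---|---|---|---|
| 450 | 9,000 (188) | 4,500 (94) | 2,250 (47) |
| 225 | 4,500 (94) | 2,250 (47) | 1,125 (23) |
| 112.5 | 2,250 (47) | 1,125 (23) | 563 (12) |

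Above these baselines ordinary change exceeds the signal; below them it is smaller.

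**Step 4: a plausible range of baselines.** Section 3.2 gives a city population of about 456 000. Assume 22% are adolescents: 0.22 × 456 000 = 100,320. Assume 0.05 to 1.0 counted visits per adolescent per year: 5,016 to 100,320 visits.

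- V = 450 is then 450 / 5,016 = 9.0% down to 450 / 100,320 = 0.4% of baseline.
- A 10% change is 502 to 10,032 visits, or 1.1 to 22 times V = 450.
- A 5% change at the lowest baseline is 251 visits, 0.56 times V, so there the signal is the larger.
- If clients made several visits each, for example 2,000 in all, V would be 2,000 / 5,016 = 40% of the lowest baseline, and a 10% change only 0.25 times V.

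**The case against.** The strongest reply is that no before/after estimator is fixed. Section 4.3.3 says the data will allow an estimate, section 6.3 specifies no analysis of it, and process data are to be triangulated with outcome data, which include voucher-based referral completion. The same sentence mentions recording Y-Check service attendances. Nothing forbids combining the sources, and the detail could be left to a later plan. This has some weight. But the text attaches a causal quantity to the aggregate counts, and the reference to service attendances may mean the check-up visits. Neither it nor the triangulation links the estimate to vouchers.

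A second reply is that vouchers answer a different question: they give gross load, not net increase. That stands, and the replacement text must say so. The aggregate series is the only planned source that touches net change, but without a comparator it cannot attribute that change.

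Four stronger readings are tempting, and the documents do not support them:

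- A reader might infer that ordinary change must swamp the referral effect. Baseline attendance and its variation are not given, and Step 4 shows the result can go either way.
- A reader might infer that vouchers count every Y-Check attendance. Only redeemed vouchers are counted, timing is listed for 0 to 4 months, the first appointment suffices for completion, and registers and self-report are needed as supplements.
- A reader might take 450 as a ceiling on visits. The 30% is illustrative, a client may have several referrals, and section 6.1 leaves out of the 450 anyone who completed some but not all. Figure 1 also lists dentists, hearing and eyesight NGOs, a physiotherapist and others besides clinics. Care given on the spot works in the opposite direction.
- A reader might infer that COVID-19 disturbed the clinic counts. Section 2.3 speaks only of effects on research activities.

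**Conclusion.** The point holds as a limit on attribution. An uncontrolled before/during/after change in aggregate counts from the referral clinics cannot be read as the effect of Y-Check referrals. This follows from the design as written and needs no assumed number.

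The size is less certain. Ordinary change may equal or exceed the referral signal: with one visit each for 450 clients and a 10% change, this happens from about 94 adolescent visits per clinic-month upwards. The reverse may hold at low-volume specialist or NGO services, or where clients make several visits. Both statements rest on assumed baselines and variation.

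The importance is minor. The estimate is a process-evaluation output; it is not among the outcomes in section 6.1, and the primary outcome is untouched. It is worth changing because the better data are already being collected.

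**What to change.** Replace the attribution clause in section 4.3.3 with wording such as: *Y-Check's contribution to clinic load will be the number of redeemed vouchers plus register-confirmed Y-Check referrals per provider-month, each referral visit counted once, shown as a share of all adolescents seen according to the aggregate routine data. This is a gross figure: it includes visits that would have happened anyway and omits spill-over, and repeat visits or visits after 4 months may be missed. Totals before, during and after implementation will be described only and will not be attributed to Y-Check referrals.*

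Numerator and denominator should use the same unit (people or visits) and the same age range. The aggregate counts keep their value as denominator and context.

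The cost is essentially wording, since vouchers, register review and aggregate counts are already planned. The price is that the net increase is no longer claimed. If the team wants it, comparison clinics and trend adjustment would have to be added. Even then, the effect of referrals would not be separated from that of training, outreach and messages.

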#### **Table 2: Process Evaluation Summary**

	Researc	ch Domain	Research Questions / Key Areas of Investigation	Data Collection Methods and Sources			
entation	What is implemented and how?	Coverage & Uptake	What proportion of adolescents accessed various components of the intervention?  How equitable was this coverage?  What were the barriers and facilitators to coverage and uptake?	Programme monitoring data  Follow-up questionnaires with clients  Structured / unstructured observations , workshops, informal interviews			
Implementation	What is implem	Fidelity	How did a) training, and b) actual implementation of each intervention component and delivery-mode vary from what was planned?  What were the barriers and facilitators to implementation fidelity?  What adaptations were made?	/ IDIs, paired/group interviews and / or FGDs with adolescents			
[mpact	lead to change?	Responses to and interactions with the intervention	Which components of the intervention were best accepted and adopted by adolescents, parents, teachers, healthcare providers, and other stakeholders?  What were the barriers and facilitators to acceptability?	Follow-up questionnaires with clients  Structured / unstructured observations			
Mechanism of Impact	How does intervention lead to change?	Interactions and Consequences	How did various components of the intervention interact?  What happened after the initial screening and referral? Were clients satisfied with the overall experience?  Were there any unanticipated pathways or consequences?	Field notes  IDIs, paired/group interviews and / or FGDs with adolescents providers, family members of adolescents, community members and other key stakeholders			
Context	How context affects implementation and shape outcomes?"	Proximal and Distal	What social, cultural, political, and logistical factors impede or facilitate (or were affected by) how the intervention was implemented, and how adolescents and other stakeholders engaged with it?  What were contextual reasons for adaptations to the intervention and its delivery?	Structured / unstructured observations  Field notes  IDIs, paired/group interviews and / or FGDs with adolescents, providers, family members of adolescents, community members and other key stakeholders			

#### **Qualitative data**

The methods for qualitative data collection will include observations, and IDIs, group/paired interviews, informal interviews, workshops and FGDs with adolescents, providers, teachers and other key stakeholders. To reduce the volume of data collection, and burden on research participants, one data collection method may provide data for several research questions simultaneously. Purposive and theoretically informed sampling will be used to determine the sampling frame for other data collection methods, with consideration of study community and provider and participant characteristics (e.g. age, gender, degree of engagement with the intervention). It is anticipated that up to 80 individual in-depth interviews with Y-Check service attendees from the 4 study communities, and up to 16 focus group discussions will be conducted. Up to 40 in-depth interviews with school and intervention staff, up to 40 in-depth interviews and focus group discussions with family members of adolescents, and up to 50 in-

depth interviews and FGDs with key informants including community members and adolescents who did not attend the intervention will be conducted. Semi-structured observations of various components of the Y-Check intervention will be conducted. Throughout the study, the process evaluation will remain flexible and dynamic to be responsive and adapt to emerging study and process findings.

